The primary outcome of this study will be the difference in mean 3-month change in tear lipid layer thickness between Systane Complete PF and Refresh Relieva PF. Fogt and colleagues were able to establish statistical significance in the differences in short-term (15 min) change from baseline in tear lipid layer thickness when comparing a lipid-emulsion to non-emulsion in two separate studies with 20 subjects (10 subjects/arm).^{3, 4} In this study we are implementing a complete 3-month treatment regimen, and additionally will increase the target sample size to N=84 (4 study arms, 21 subjects/arm), and therefore can be reasonably assured of having sufficient statistical power to detect any treatment-control differences that may present.

Surveys and Clinical Tests

Clinical measurements will be obtained from both eyes of each subject and testing will be performed in the below order. Testing order was designed to sequentially administer the least invasive to most invasive test. This methodology will ensure that a previous procedure will have a minimal effect on subsequent assessments

Study Visit

A. Baseline/Screening Visit

(Visit 1A)

1. Subject History, Eligibility, Informed Consent: Subjects will be asked to repeat the IRB approved screening survey at the study visit to verify that they are still eligible for the study. Non-eligible subjects will be dismissed or rescheduled depending upon the reason for ineligibility. Eligible subjects will be enrolled, consented, and requested to sign a privacy document.

2. Baseline Questionnaires: Subjects demographics, lifestyle, ocular and medical history will be collected. They will be asked to complete the PSQ, Likert, DEFC, SPEED II, OSDI, VAS, SANDE, and DEQ-5 questionnaires to determine baseline comfort.

(Visit 1B)

1. Baseline Visual Acuity: The subject's habitual visual acuity will be measured.

2. Tear Lipid Layer Thickness and Blinks: The Lipiview interferometer will be used to determine the subject's tear lipid layer thickness and blinks.

3. Tear Meniscus Height, Ocular Redness, and Keratometry: The Oculus Keratograph 5M will be used to determine the tear meniscus height, redness, and curvature of the eyes.

4. Non-Invasive Tear Breakup Time (NITBUT): The Oculus Keratograph 5M and Medmont Topographer will be used to determine NITBUT with the machine's standard software by taking one to three successive measurements.

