5. Slit-Lamp Biomicroscopy: The investigator will use a slit-lamp biomicroscope to document normal and/or remarkable findings of the anterior eye structures: eyelashes (blepharitis), eyelids, conjunctiva, and cornea.

6. Fluorescein Tear Breakup Time (FTBUT): The investigator will instill 1 μ l of 1% w/v of sodium fluorescein by pipette and take 3 successive measurements for each eye.

7. Slit Lamp Recordings with EasyTear View: Capture videos with diffuse white light and cobalt blue light to analyze tear film lipids (thickness and uniformity) and tear film thinning dynamics.

8. Schirmer's Test: Investigator will use a modified technique³ for aqueous tear production rate measurement.

9. Meibomian Gland Expression: The investigator will use the Korb Meibomian gland expressor to apply pressure along both the upper and lower eyelids and score gland secretion quality on central/nasal/temporal regions of each lid (i.e., ~5 glands in each region) with scores ranging from 0-3 (0=no secretion, 1=inspissated, 2=cloudy, 3=clear), such that each lid will have a maximum score of 45.

10. Lissamine Green Evaluation: The investigator will evaluate the quality of the front surface of the eyes by instilling a small amount of lissamine green ophthalmic dye.

11. Meibography: The Oculus Keratograph 5M will be used to image the tear glands (e.g., Meibomian glands) of the upper and lower eyelids.

12. Dispense Run-In Drops and Instructions: Investigators will dispense one week's worth of Systane Ultra PF (label removed) to all qualified, enrolled subjects and instruct them to instill drops 4 times daily for one week. Patients are then scheduled for their next visit at least 90 minutes after their planned last dose.

B. Visit 2: Post-Run-In Period, Randomization, Treatment

1. Subject History: Subjects will be asked to confirm any changes to medical or ocular history.

2. Questionnaires: Subjects will be asked to complete an abbreviated questionnaire package to determine comfort.

3. Visual Acuity: The subject's habitual visual acuity will be measured.

4. Tear Lipid Layer Thickness and Blinks: The Lipiview interferometer will be used to re-assess the subject's tear lipid layer thickness and blinks.

5. Tear Meniscus Height, Ocular Redness, and Keratometry: The Oculus Keratograph 5M will be used to determine the tear meniscus height, redness, and curvature of the eyes.

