6. Non-Invasive Tear Breakup Time (NITBUT): The Oculus Keratograph 5M will be used to determine NITBUT with the machine's standard software by taking three successive measurements.

7. Slit-Lamp Biomicroscopy: The investigator will use a slit-lamp biomicroscope to document normal and/or remarkable findings of the anterior eye structures: eyelashes (blepharitis), eyelids, conjunctiva, and cornea.

8. Fluorescein Tear Breakup Time (FTBUT): The investigator will instill 1 μ l of 1% w/v of sodium fluorescein by pipette and take 3 successive measurements for each eye.

9. Slit Lamp Recordings with EasyTear View: Capture videos with diffuse white light and cobalt blue light to analyze tear film lipids (thickness and uniformity) and tear film thinning dynamics.

10. Confocal Microscope: The confocal microscope will be used to examine anatomy and physiology of the front surface of the eyes.

11. Randomize, Dispense Study Drops, and Instructions: Subjects will be randomized to one of four study drops (Refresh Relieva PF, Systane Complete PF, Refresh Optive Mega-3 PF, or CVS Health Lubricant Eye Drop (PG 0.6%)). Investigators will dispense a 1-month supply of the assigned study drops and provide instructions to instill drops 4 times daily for 3 months. Patients are then scheduled for their 1-month follow-up visit, ensuring visit is scheduled at least 90 minutes after their planned last dose.

C. Visit 3: One Month Follow-Up

1. Repeat measurements (Part B) 1-9 and 11 from baseline visit.

2. Dispense study drops. The investigator will dispense drops for the next two months and schedule the follow-up phone call at 2 months and the final visit at 3 months.

D. Phone Call: Two Month Follow-Up

1. Subject History: Subjects will be asked to confirm any changes to medical or ocular history.

2. Follow-up to ensure no changes in habitual regimen, protocol is being followed, supply of drops is adequate to reach the end of the study.

3. Questionnaires: Subjects will be asked to complete an abbreviated questionnaire package to determine comfort.

E. Visit 4: Three Month Follow-Up

1. Repeat measurements (Part B) 1-10 from baseline visit.

2. Exit Visual Acuity: The subject's habitual visual acuity will be measured.

3. Study Completion: Subjects will be compensated for their time and exited from the study.

F. Schedule of Study Procedures and Assessments

Procedure/Assessment	Visit 1	Visit 2	Visit 3	Phone Call	Visit 4
Inclusion/Exclusion	✓				
Informed Consent	✓				

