Demographics	✓				
Medical and Ocular History	✓	✓	✓	✓	✓
PSQ, Likert, DEFC, SPEED II, OSDI, VAS, SANDE, & DEQ-5	✓	✓	✓	✓	✓
Randomization		✓			
Visual Acuity	✓	✓	✓		✓
Tear Lipid Layer Thickness and Blinks	✓	✓	✓		✓

Tear Meniscus Height, Ocular Redness and Keratometry	✓	✓	✓		✓
Non-Invasive Tear Breakup Time	✓	✓	✓		✓
Slit-Lamp Exam	✓	✓	✓		✓
Fluorescein Tear Breakup Time	✓	✓	✓		✓
Easy TearView Recordings	✓	✓	✓		✓
Schirmer's Test	✓		✓		✓
Meibomian Gland Expression	✓				✓
Lissamine Green Evaluation	✓				
Meibography	✓				
Confocal Microscope		✓			✓
Adverse Events		✓	✓	✓	✓
Exit					✓

Data Analysis

Primary Model (Aim 1):

- The primary outcome of tear lipid layer thickness (LipiView) change from post-run-in baseline to 3 months will be analyzed using a repeated measures mixed effects model. This modeling approach will produce an unbiased estimate of the treatment effects (Systane Complete PF vs. Refresh Relieva PF), while accounting for the internal correlations engendered by the repeated measures study design (repeat visits, two eyes per subject).

Additional Analyses (Aims 2-5, Exploratory):

- The same modeling approach will be employed to analyze the changes from post-run-in baseline to 3 months in tear lipid layer uniformity and in tear thinning time between the Treatment (Systane Complete PF) and Control (Refresh Relieva PF) solutions.
- The same modeling approach will be employed to analyze changes from post-run-in baseline to 3 months in lipid layer thickness and uniformity, tear thinning time, and symptom scores among 3 solutions (Systane Complete PF, Refresh Optive Mega-3 PF, CVS Health Lubricant Eye Drop (PG 0.6%)).
- Additional exploratory modeling for all outcomes will be performed to determine the impact of baseline subject characteristics including demographics, visual acuity, tear film stability (NITBUT and FTBUT), tear production (Schirmer's), and any ocular surface findings.
- Exploratory models will be assessed by F-test p-values, residual and other diagnostic plots, fit statistics such as the log-likelihood and the AIC, and clinical relevance of effect sizes. Both additive and interaction models will be examined.

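### The primary change-score model does not pre-specify post-run-in baseline lipid layer thickness as a covariate, which would usually add precision at 21 per arm

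*Combined protocol and SAP*

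**What the plan says.** Under Data Analysis, Primary Model (Aim 1), "tear lipid layer thickness (LipiView) change from post-run-in baseline to 3 months will be analyzed using a repeated measures mixed effects model". The model is described as "accounting for the internal correlations engendered by the repeated measures study design (repeat visits, two eyes per subject"), and the contrast is Systane Complete PF against Refresh Relieva PF. No covariate is mentioned. The Sample Size section likewise defines the primary outcome as the "difference in mean 3-month change in tear lipid layer thickness between Systane Complete PF and Refresh Relieva PF".

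Baseline variables appear only under Additional Analyses, where exploratory models will look at the "impact of baseline subject characteristics including demographics, visual acuity, tear film stability (NITBUT and FTBUT), tear production (Schirmer's), and any ocular surface findings". Baseline lipid layer thickness is not named there, although the list is open-ended.

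At Visit 2, step 4, "The Lipiview interferometer will be used to re-assess the subject's tear lipid layer thickness and blinks". At step 11 of the same visit, "Subjects will be randomized to one of four study drops". The Surveys and Clinical Tests section says that tests follow the listed order, so the baseline thickness value precedes allocation.

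**The concern.** Analysing change without baseline in the model fixes the slope of the 3-month value on baseline at exactly 1. When the true slope is below 1, which is usual for a measurement with error, the change score over-corrects and carries avoidable variance. It also leaves a conditional error. With equal SDs at the two visits and correlation rho between them, a chance baseline difference between arms shifts the estimated treatment effect by -(1 - rho) times that difference.

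The primary comparison is 21 against 21, and the plan gives no alpha, SD, effect size or power for it, so precision is not obviously to spare. A second, smaller point is that if the primary text is read as silent on covariates, the choice between an adjusted and an unadjusted result could be made after the data are seen.

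**Working it through.** **The plan's own figure.** The 84 subjects (21 in each of 4 arms) cannot be reproduced, because no alpha, effect size, SD, power or dropout rate is given.

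**Inputs.** From the documents: 21 per arm in the primary comparison, baseline measured before randomisation, change as the response. Assumed: two-sided alpha 0.05, complete data, one value per subject (mean of two eyes), one follow-up, and a range for rho.

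**Detectable difference as planned.** Noncentral t, 40 df: 80% power needs a difference of 0.886 change-SD.

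**Variance ratio, equal SDs.** With common SD s:
- Change score: 2s²(1 - rho).
- Baseline-adjusted: s²(1 - rho²).
- Ratio: (1 + rho)/2, times 1 + 1/(2 × 21 - 4) = 39/38 for estimating the slope.

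At rho 0.5 this is 0.75 × 39/38 = 0.770. Adjusted power uses 39 df at the difference where the unadjusted analysis has 80%.

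| rho | Variance ratio | Adjusted power | 80%-power difference (change-SD) |
|---|---|---|---|
| 0.3 | 0.667 | 93% | 0.72 |
| 0.5 | 0.770 | 89% | 0.78 |
| 0.7 | 0.872 | 85% | 0.83 |
| 0.8 | 0.924 | 83% | 0.85 |
| 0.9 | 0.975 | 81% | 0.875 |
| 0.95 | 1.001 | 80% | 0.887 |

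Break-even is rho = 2 × 38/39 - 1 = 0.949. In sample-size terms, 21/0.770 = 27 per arm at rho 0.5 and 21/0.872 = 24 at rho 0.7. A simulation of 20,000 trials per value of rho gave ratios of 0.66, 0.78, 0.87, 0.98 and 1.00 at rho 0.3, 0.5, 0.7, 0.9 and 0.95.

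**Unequal SDs.** With k = 3-month SD / baseline SD, the ratio is k²(1 - rho²)/(1 + k² - 2 rho k) × 39/38.

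| rho | k = 1.25: ratio (power) | k = 0.8: ratio (power) |
|---|---|---|
| 0.3 | 0.81 (88%) | 0.52 (97%) |
| 0.5 | 0.92 (83%) | 0.59 (96%) |
| 0.7 | 1.01 (80%) | 0.64 (94%) |
| 0.8 | 1.026 (79%) | 0.66 (93%) |
| 0.9 | 0.975 (81%) | 0.62 (94%) |

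At k = 1.25 there is no gain between rho of about 0.68 and 0.88. The worst case is a true slope of exactly 1 (rho × k = 0.8 × 1.25), where the ratio is 39/38 = 1.026.

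**Chance imbalance, equal SDs.** The SE of the baseline difference is sqrt(2/21) = 0.309 baseline-SD; a difference of 1 SE or more arises in about 32% of randomisations. A 1-SE difference shifts the change-score estimate by (1 - rho) × 0.309 = 0.154, 0.093 and 0.031 baseline-SD at rho 0.5, 0.7 and 0.9. Against change-score SEs of 0.309, 0.239 and 0.138, that is 0.50, 0.39 and 0.22 of an SE.

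**Two eyes.** The form of the covariate matters. In a simulation of 6,000 trials, 70% of the variance was assumed to lie between subjects, with a between-subject correlation of 0.8 and no correlation over time in the eye deviations. The variance ratio was 0.84 with the subject mean and 0.92 with the same-eye value alone. With both correlations at 0.5, the ratios were 0.77 and 0.76.

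**The case against.** The planned analysis is valid. A randomised comparison of change scores is unbiased with correct type I error, and it matches the stated outcome, so the plan's claim of an unbiased estimate stands. That is accepted: this is a choice between two valid estimators.

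The natural reading of the text may also be an unadjusted primary model with all covariates left to exploratory work. On that reading the analytic choice is closed and only the efficiency argument remains. This is fair, and the pre-specification argument should carry little weight alone. On either reading, however, baseline thickness is not a pre-specified primary covariate.

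The gain cannot be determined from the documents. It is at most about 3 points of power from rho 0.8 upward with equal SDs, and nil or slightly negative over part of the range if the SD grows. The figures also simplify the planned model to one value per subject and one follow-up, and the two-eye simulation adds assumed inputs. All of this stands. It limits what can be promised but does not reverse the advice, since in the cases examined the loss never exceeds 2.6% of variance while the gain can be a third or more.

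Finally, it might be said that a mixed model already handles baseline. It does not here: change is the response, modelling the correlation of changes across visits and eyes does not estimate a baseline slope, and no common baseline mean is stated.

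**Conclusion.** The concern holds as a point of efficiency and, secondarily, of pre-specification; it does not threaten validity. With equal SDs, adjustment reduces the variance of the primary contrast by about 33% at rho 0.3, 23% at 0.5, 13% at 0.7 and 2.5% at 0.9, with break-even near 0.95. If the 3-month SD is a quarter larger than baseline, the gain is smaller and can disappear; if it is a fifth smaller, the gain is larger throughout. All these sizes rest on an assumed rho and SD ratio, a two-sided 0.05 test and complete data on 21 per arm. The change is worth making because the covariate is already collected and the possible loss is about one point of power.

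**What to change.** In the Primary Model paragraph, pre-specify post-run-in baseline LipiView thickness as a covariate. State how it enters: either as the subject mean over both eyes, or as the same-eye value together with the subject mean, so that the between-subject slope is used. Include arm, visit, arm-by-visit and baseline-by-visit terms, keep the planned subject and eye correlations, and name the 3-month Systane Complete PF minus Refresh Relieva PF contrast as the primary result. A longitudinal model with baseline as a response and a common baseline mean across arms is an acceptable equivalent. Because the plan applies the same modelling approach to the other change endpoints, the same form can serve them, each with its own baseline; this extension is desirable but secondary.

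The cost is SAP wording. No visit, test or subject is added. The figures above already charge one degree of freedom for the slope; entering a same-eye term as well would use one more.
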